#### **7.4 Efficacy Assessments**

Subjects who began non-flare-up-based treatment during Part B will continue the same visit schedule into Part C, and will receive non-flare-up-based treatment for up to an additional 48 months. Therefore, these subjects may undergo non-flare-up-based treatment for up to 72 months over the entire study. Subjects who will start non-flare-up-based treatment during Part C will receive non-flare-up-based treatment for up to 48 months.

##### **7.4.1 Low-Dose Whole Body Computed Tomography**

For subjects from Part B continuing non-flare-up-based treatment into Part C, a low-dose WBCT scan (excluding head) will be performed during annual site visits at Months 12, 24, 36, 48, 60 and 72.

For subjects from Part B starting non-flare-up-based treatment during Part C, a low-dose WBCT scan (excluding head) will be performed at Part C Screening and during annual site visits at Months 12, 24, 36 and 48.

For subjects in Part D, a low-dose WBCT scan (excluding head) will be performed during annual site visits at Y1 and Y2 post last dose of study treatment.

Interpretation of the CT scan will document the absence or presence of HO across various body regions, volume of total body HO, and presence and volume of new HO at follow-up visits. All images will be interpreted by a central imaging core laboratory using standardized procedures detailed in an imaging charter.

##### **7.4.2 FOP-Physical Function Questionnaire**

On clinic days when multiple assessments are to be performed, the age-appropriate FOP-PFQ and the age-appropriate PROMIS Global Health Scale should be completed (in that order) by the

subject/parent before any other procedures are completed on those visit days.

For subjects from Part B continuing non-flare-up-based treatment into Part C, age-appropriate forms of the FOP-PFQ will be administered every 6 months (Months 6, 12, 18, 24, 30, 36, 42, 48, 54, 60, 66 and 72).

For subjects from Part B starting non-flare-up-based treatment during Part C, age-appropriate forms of the FOP-PFQ will be administered at Part C Screening and every 6 months (Months 6, 12, 18, 24, 30, 36, 42 and 48).

To evaluate the effect of palovarotene on physical function, age-appropriate forms of the FOP-PFQ will be administered. The adult form of the FOP-PFQ will be completed by subjects 15 years of age and older (see [Appendix 2A](#)). Two Pediatric FOP-PFQ (FOP-PFQ-P) forms will be utilized in subjects under the age of 15 years: a self-completed form developed for 8- to 14-year-olds and a proxy-completed form developed for 5- to 14-year-olds (see [Appendix 2B](#) and [Appendix 2C](#), respectively).

Study personnel will be trained on the administration of the instruments and subjects (and parents of subjects under the age of 15 years) will be provided specific instructions on how to complete the instrument independently.

#### **7.4.3 PROMIS Global Health Scale**

For subjects from Part B continuing non-flare-up-based treatment into Part C, age-appropriate forms of the PROMIS Global Health Scale will be administered every 6 months (Months 6, 12, 18, 24, 30, 36, 42, 48, 54, 60, 66 and 72).

For subjects from Part B starting non-flare-up-based treatment during Part C, age-appropriate forms of the PROMIS Global Health Scale will be administered at Part C Screening and every 6 months (Months 6, 12, 18, 24, 30, 36, 42 and 48).

To evaluate the effect of palovarotene on physical and mental health in subjects  $\geq 15$  years of age and mental health in subjects  $< 15$  years of age, age-appropriate forms of the PROMIS Global Health Scales will be administered. The adult form of the PROMIS Global Health Scale will be administered to subjects 15 years of age and older (see [Appendix 7A](#)). Two PROMIS Pediatric Global Health Scale forms will be utilized in subjects under the age of 15 years: a self-completed form developed for 8- to 14-year-olds and a proxy-completed form developed for subjects under the age of 15 years (see [Appendix 7B](#) and [Appendix 7C](#), respectively).

Study personnel will be trained on the administration of the instruments and subjects (and parents of subjects under the age of 15 years) will be provided specific instructions on how to complete the instrument independently.

#### **7.4.4 Cumulative Analogue Joint Involvement Scale**

For subjects from Part B continuing non-flare-up-based treatment into Part C, CAJIS will be administered every 6 months (Months 6, 12, 18, 24, 30, 36, 42, 48, 54, 60, 66 and 72).

For subjects from Part B starting non-flare-up-based treatment during Part C, CAJIS will be

administered at Part C Screening and every 6 months (Months 6, 12, 18, 24, 30, 36, 42 and 48).

Range of motion will be assessed by the Investigator using CAJIS (see [Appendix 1](#)). The CAJIS should be assessed by the same Investigator at each time point. The CAJIS assessment may be performed remotely or by videoconferencing.

## **7.5 Pharmacokinetics**

The PK of palovarotene dosing will be assessed in all subjects during non-flare-up and flare-up-based treatments.

During non-flare-up palovarotene treatment, PK blood samples will be collected at the first 3-month safety assessment. If blood samples cannot be or were not obtained during the first 3-month safety assessment, or if the subject is on flare-up-based treatment, then the non-flare-up treatment PK blood sample can be obtained during any subsequent 3-month safety visit.

Pharmacokinetics of palovarotene dosing will also be assessed twice during flare-up-based treatment: once during the 20-mg regimen at any time between Study Days 4 to 28, and once during the 10-mg regimen at any time between Study Days 32 to 84, for the first treated flare-up only. If this is not possible for the first treated flare-up, PK blood samples can be obtained during any subsequent flare-up dosing cycle.

Pharmacokinetic blood samples will be collected at pre-dose and 3, 6, 10, and 24 hours post-dose. Subjects who underwent a PK assessment for flare-up-based treatment under PVO-1A-202 Protocol Amendment 3 will not have flare-up PK assessed again. However, these subjects will require a non-flare-up treatment PK assessed at a 3-month safety visit.

The determination of palovarotene plasma concentrations will be performed using a validated LC-MS/MS method, and exploration of any relationships with palovarotene exposure will be performed. The time of sample collection as it relates to the time of dosing on the PK blood sampling days will be recorded.

Detailed instructions for collection, storage, labeling, and shipment of all samples will be provided in the Laboratory Manual.

## **7.6 Data Monitoring Committee**

A Data Monitoring Committee (DMC) will review safety information periodically and on an ad hoc basis as outlined in the DMC Charter, which is maintained separately from the study protocol. The DMC can recommend temporary or permanent stopping of the study at any time if there are significant safety concerns. The DMC Charter includes recommended safety stopping rules. The DMC will also review the results of pre-planned interim analyses (see Section 8.7). In addition to the Investigator, the DMC will make recommendations for potential dose modifications in the event of treatment-related adverse bone effects as described in the Bone Safety Management Plan.

The DMC will include members with relevant clinical expertise, including a good understanding of the safety of retinoids. The methodology and the operating procedures for the safety reviews

will be developed by the Chairperson in collaboration with the sponsor and will be documented in the DMC Charter.

## 7.7 Temporary Measures (Procedures Related to COVID-19 Pandemic)

### Procedures related to COVID-19 pandemic

Temporary measures put in place for the conduct of Study PVO-1A-202 during the COVID-19 pandemic and until such time as the situation resolves, at which point the protocol assessments will return to those specified. Investigators will determine the feasibility of dosing on a subject-by-subject basis, depending on the ability to conduct safety monitoring and providing subjects an adequate supply of study drug, in accordance with local requirements. These recommendations will remain in place for as long as the COVID-19 pandemic warnings are in effect in territories participating in the trial. The timing of when the pandemic is declared over may vary on a country-by-country basis as well as between sites in the same country, and as such the temporary measures may remain in place for differing periods of time per country/site.

The study visits and assessments to be conducted during this period are listed below:

#### Study Visits and Assessments

- 1) **For subjects aged under 14 years that are still participating in the study but not currently receiving palovarotene treatment as per the global partial clinical hold or for any other reason**, they will complete Part C EOT/EOS and be invited to participate in Part D and undergo assessments outlined in [Table 4](#).
- 2) **For subjects aged 14 years and older who are being considered for re-starting palovarotene treatment but have NOT yet re-started**, the following minimum assessments are to be done via remote monitoring (video conference/phone calls) by the Investigator (or delegated study staff):
  - a. Chronic visits every 3-6 months (per protocol): assess for childbearing status (females only) and pregnancy prevention measures, CAJIS, ConMeds, adverse events, review subject diary, PROMIS Global Health Scale\*, FOP-PFQ\* (\*assessments that can occur remotely but not required as these are not essential to ensure subjects' safety)
  - b. For females of childbearing status: if pregnancy testing did not continue monthly per protocol post the study drug interruption then at a minimum a self-administered urine pregnancy test is to be done within 4 weeks before re-starting palovarotene treatment.
  - c. All subjects should have laboratory assessments (hematology, biochemistry, urinalysis) within 4 weeks before re-starting palovarotene treatment.
  - d. All subjects who were skeletally immature at the last assessment will have a hand-wrist and knee radiographs within 12 weeks before re-starting palovarotene treatment. For on-treatment subjects who have not reached at least 90% skeletal maturity radiograph assessments should continue per protocol either on site or remotely

Site staff will also assess the subject's ability to restart remotely.

3) **For subjects 14 years and over that plan to reinitiate dosing, once dosing is reinitiated following the required approvals for restart (Ethics Committee and Competent Authority), the following minimum assessments that cannot be performed via remote monitoring must be performed either at the clinical site, at the subject's home (by Symphony nursing) or at a local medical facility in order for the Investigator to adequately monitor the safety of subjects:**

- a. Via remote monitoring (telephone or video conferencing) by Investigator (or delegated study staff):
  - i. Chronic visits (per protocol schedule every 3 and/or 6 months): C-SSRS, assess for childbearing status (females only) and pregnancy prevention measures, CAJIS, ConMeds, adverse events, PROMIS Global Health Scale\*, FOP PFQ\* (\*assessments that can occur remotely but are not required as these are not essential to ensure subjects' safety), study drug dispensing
  - ii. Flare up visits (per protocol schedule): C-SSRS, ConMeds, adverse events, study drug dispensing
- b. Via home visit by Symphony nursing/local assessment
  - i. Chronic visits per protocol schedule (every 3 and/or every 6 months): body weight, vital signs, hematology, biochemistry, urinalysis, self-administered pregnancy test (monthly), ConMeds, adverse events, review subject diary
  - ii. Flare up visits (per protocol schedule): vital signs, body weight, hematology, biochemistry, urinalysis, self-administered pregnancy testing, ConMeds, adverse events, review subject diary

4) **Based on the known safety profile of palovarotene to date in FOP patients, the following assessments can be postponed as determined by the Sponsor and individual site Investigators, as they do not constitute assessments where a safety concern has been raised.**

The below assessments were also deemed acceptable to postpone by the DMC chair.

- a. To date low dose whole-body CT has not indicated a safety concern of avascular necrosis of the hip. Any concerns for avascular necrosis of the hip based on clinical assessment should be followed up;
- b. For subjects who have reached at least 90% skeletal maturity radiograph assessments may be postponed given the low risk of early growth plate closure as well as growth plate abnormalities;
- c. Linear height and knee height (Subjects 14 years and older are at or near adult height indicated by skeletal maturity of at least 90%);
- d. ECG (FOP patients can have ECG abnormalities, ECG changes noted in subjects on Palovarotene were similar to those seen in the untreated subjects in the Natural History Study. Clinical concerns of abnormal ECG findings should continue to be followed);
- e. Hearing evaluation (As a class, retinoids can cause abnormal hearing. Evaluation should be performed if there is clinical concern);
- f. Physical exam (Palovarotene has been shown to cause retinoid skin reactions which can be assessed remotely)

Individual subjects may require assessments if there is a clinical concern as identified by the Investigator. Protocol deviations that have an impact on subject safety should be notified immediately to CRO/Sponsor as it may necessitate an urgent safety measure notification to competent authorities and ethics committees in some countries.

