### 5.2.2 Exclusion Criteria

- 1 Weight <20 kg.
- 2 Intercurrent known or suspected non-healed fracture at any location.
- 3 Currently using vitamin A or beta carotene, multivitamins containing vitamin A or beta carotene, or herbal preparations, fish oil, and unable or unwilling to discontinue use of these products during palovarotene treatment.
- 4 Exposure to synthetic oral retinoids other than palovarotene in the past 30 days prior to Part B Screening (signature of the informed consent).
- 5 Concurrent treatment with tetracycline or any tetracycline derivatives due to the potential increased risk of pseudotumor cerebri.
- 6 History of allergy or hypersensitivity to retinoids or lactose.
- 7 Concomitant medications that are inhibitors or inducers of cytochrome P450 (CYP450) 3A4 activity (see Section 5.6).
- 8 Amylase or lipase >2x above the upper limit of normal (ULN) or with a history of chronic pancreatitis.
- 9 Elevated aspartate aminotransferase (AST) or alanine aminotransferase (ALT) >2.5x ULN.
- 10 Fasting triglycerides >400 mg/dL with or without therapy.
- 11 Female subjects who are breastfeeding.
- 12 Subjects with uncontrolled cardiovascular, hepatic, pulmonary, gastrointestinal, endocrine, metabolic, ophthalmologic, immunologic, psychiatric, or other significant disease.
- 13 Subjects experiencing suicidal ideation (type 4 or 5) or any suicidal behavior within the past month as defined by the Columbia Suicide Severity Rating Scale (C-SSRS).

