### **5.7 Subject Withdrawal or Early Termination from Study**

Subjects can voluntarily withdraw from the study at any time for any reason. All reasonable effort should be made by the study personnel to determine the reason for withdrawal. Subjects will be considered lost to follow-up if no response is received in spite of repeated attempts to contact them.

Study drug administration for individual subjects can be discontinued by the Investigator if he/she believes the subject's safety is at risk. Additional details regarding study drug dose modification are provided in [Section 6.5](#).

If any subject enrolled in Part D chooses to enroll in another clinical trial, all reasonable efforts should be made by the study personnel to have the subject continue participation in Study PVO-1A-202 until their final EOS visit.

In the event of an early termination or discontinuation of study drug, all reasonable efforts should be made by the study personnel to have the subject complete all study assessments per the Schedule of Assessments for non-flare-up-based treatment ([Table 1](#) and [Table 2](#)), and if appropriate, for flare-up-based treatment ([Table 3](#)), including those assessments subsequent to early termination or study drug discontinuation.

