### **7.3.3 Bone Safety Management Plan**

To enhance subject safety monitoring, a Bone Safety Management Plan has been developed to supplement per-protocol safety monitoring. Of note, in addition to the knee and hand/wrist radiographs described in Section 7.3.2, WBCT scans acquired from subjects under the age of 18 years will be reviewed in a blinded fashion by two independent radiologists to assess the growth plate morphology of bilateral hands/wrists and knees. Reviews of WBCT scans from all subjects regardless of age will also monitor hip morphology for signs of avascular necrosis (AVN), warranted due to the association of corticosteroids with AVN and the presence of AVN of the femoral head in wild-type rats treated with high dose palovarotene. WBCT scans will be reviewed for spinal health including fracture assessment.

The Bone Safety Management Plan will be provided to each clinical site, must be signed by the clinical site Investigator, and will be appended to the Data Monitoring Committee Charter.

Safety findings of these bone images may trigger additional follow-up images and/or dose

modification, as discussed in the Bone Safety Management Plan.

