**5) End of Treatment/End of Study Assessments:**

- a. The following assessments should be performed via remote monitoring (telephone or video conferencing) by Investigator (or delegated study staff):
  - i. C-SSRS, assess for childbearing status (females only) and pregnancy prevention measures, CAJIS, Con-Meds, adverse events, PROMIS Global Health Scale, FOP PFQ
- b. The following assessments should be performed at the subject’s home (by Symphony nursing) or at a local medical facility: Body weight, vital signs, hematology, biochemistry, urinalysis, pregnancy test (monthly), ConMeds, adverse events, review subject diary

**6) Once on-site visits resume, the following assessments should be performed on site as well as any assessment that was not obtained via remote monitoring or Symphony nurse:**

- a. X-rays, Whole-Body CT, Linear and Knee Height, Physical Exam, ECG.

**7) Informed Consent/Subject Communication:** In consultation with their site IRB/EC, Investigators are required to inform subjects of the temporary changes (during the COVID-19 global pandemic) to the study conduct and monitoring plans that could impact them and their willingness to continue participation in the trial. The method of communication to subjects (e.g., email, phone call, information letter) and documentation of subject/caregiver acknowledgement is to be performed and documented in accordance with local regulations/EC requests and guidance. All contacts with subjects must be filed in the source records.

A risk mitigation assessment will be performed for each subject at the site in order to determine how their participation may be impacted. Sites must ensure that appropriate measures are taken to ensure the safety of FOP subjects in light of the ongoing COVID-19 pandemic, taking into consideration local Ethics Committee and Competent Authority guidance, as well as the ability of individual Investigators and sites to adequately monitor subject safety.

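### The Part C criteria and the section 7.7 restart checks drop the Part B bar on dosing breastfeeding subjects and, less critically, the bar for uncontrolled significant disease

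*Protocol*

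**What the plan says.** **Part B.** PVO-1A-202 has two lists of conditions that bar dosing. Section 5.2.2 (13 items) covers daily treatment in the Adult Cohort, and section 5.3.2 (14 items) covers flare-up treatment in both cohorts. In each list, no. 11 is breastfeeding and no. 12 is uncontrolled significant disease of any major organ system.

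**Part C.** Part C has its own lists. Section 5.4.2 (all subjects) has two items: inability to comply, and use of vitamin A, beta carotene or fish oil. Section 5.5.2 (subjects first starting daily treatment in Part C) has four: pancreatic enzymes or chronic pancreatitis, transaminases, triglycerides, and suicidality.

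**Restart.** Section 7.7 item 2 is addressed as follows: "For subjects aged 14 years and older who are being considered for re-starting palovarotene treatment but have NOT yet re-started". Its minimum assessments are:
- (a) remote review of childbearing status, pregnancy prevention, CAJIS, concomitant medications, adverse events and diary;
- (b) a self-administered urine pregnancy test within 4 weeks of restart, "if pregnancy testing did not continue monthly per protocol post the study drug interruption";
- (c) laboratory tests within 4 weeks;
- (d) hand-wrist and knee films for subjects who were skeletally immature at the last assessment.

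**General cover.** Section 7.7 also says that "Investigators will determine the feasibility of dosing on a subject-by-subject basis, depending on the ability to conduct safety monitoring", and item 7 adds that "A risk mitigation assessment will be performed for each subject at the site in order to determine how their participation may be impacted". Under section 5.7, "Study drug administration for individual subjects can be discontinued by the Investigator" where safety is thought to be at risk.

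PVO-1A-204 is built the same way, except that its 5.4.2 has only the compliance item.

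**The concern.** Eligibility lists are applied at entry, but these two conditions can arise afterwards, including while a subject is off drug. Breastfeeding is the sharper case. The sponsor treated it as an absolute bar to dosing in Part B, for both daily and flare-up treatment. Part C asks only that the subject is not pregnant, and a subject who has delivered and is breastfeeding will normally pass that test. Item 2b itself allows for monthly testing having lapsed during the interruption.

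Uncontrolled disease is less critical. It is more likely to show in the adverse event, medication and laboratory review that item 2 requires, but no stated result of that review defers a restart.

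What is at stake is individual safety: a subject could be given a retinoid in a state for which the sponsor's own earlier rule withheld it. The documents do not quantify the risk to a nursing infant. The argument rests on the sponsor's Part B rule having disappeared without a stated reason, not on an outside estimate of harm.

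**Working it through.** No formula or power figure is involved. The check is an item-by-item comparison.

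**1. Where the two exclusions appear**

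| Place | Items | Breastfeeding | Uncontrolled disease |
|---|---|---|---|
| 5.2.2, Part B daily (both protocols) | 13 | no. 11 | no. 12 |
| 5.3.2, Part B flare-up (both protocols) | 14 | no. 11 | no. 12 |
| 5.4.2, PVO-1A-202 | 2 | absent | absent |
| 5.4.2, PVO-1A-204 | 1 | absent | absent |
| 5.5.2 (both protocols) | 4 | absent | absent |
| 7.7 item 2 (both protocols) | a to d | absent | absent |

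Each exclusion is in 2 of 2 Part B lists and in 0 of 3 later places, in each protocol.

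**2. Whether the Part B lists still operate.** Sections 5.2 and 5.3 of PVO-1A-202 are headed Part B; in PVO-1A-204 they are headed original protocol and Amendment 1. The flare-up rules show that they have been superseded: 5.3.1 requires at least two symptoms, whereas section 3.1 now requires only one. A site cannot assume that 5.3.2 still governs dosing.

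**3. Whether Part C dropped exclusions as a general policy.** Of the 13 items in 5.2.2, eight have a counterpart outside the Part B lists:
- vitamin A and related products, oral retinoids, tetracyclines, and CYP3A4 inhibitors or inducers (5.6.1);
- amylase/lipase, transaminases and triglycerides (5.5.2, 7.3.5 to 7.3.7);
- suicidality (5.5.2, 7.3.1).

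That leaves 13 − 8 = 5. Weight below 20 kg is moot now that dosing under age 14 has stopped. Hypersensitivity matters little in subjects already exposed. Fracture is taken up under the objection. The other two are breastfeeding and uncontrolled disease. No reason is given for omitting them.

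**4. A subject followed through the text.** Take a subject aged 14 or over who has delivered and is breastfeeding.
- Section 7.2.7 stops drug at a positive test and follows the pregnancy. It does not say when drug may resume.
- Section 5.4.1 no. 3 needs a negative pregnancy test, which she has, plus abstinence or contraception, which she can meet.
- Neither item of 5.4.2 applies to her.
- In 7.7 item 2, childbearing status and contraception are reviewed under (a), the urine test is negative under (b), and laboratory tests are done under (c). Breastfeeding is not an adverse event, a medication or a laboratory value, so nothing in (a) to (d) asks about it.

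Result: every written criterion is met. Under 5.2.2 or 5.3.2 no. 11 she would have been barred. The same holds for a Part C flare-up start, which section 3.1 has begin immediately on Investigator confirmation.

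**5. Uncontrolled disease.** Item 2c requires laboratory tests but sets no threshold for restart. The 5.5.2 limits apply to subjects starting daily treatment in Part C, and the lipid and liver rules in 7.3.5 and 7.3.6 act during treatment.

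**The case against.** The strongest reply is that restart is already well controlled. Much of it stands.

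- **A reader might infer that nothing in the protocol defers a restart at age 14 or over.** The documents do not support that. Section 5.4.1 requires a negative pregnancy test before administration, 5.6.1 calls for wash-outs after tetracyclines and strong CYP3A4 inhibitors, and 7.7 item 3 refers to Ethics Committee and Competent Authority approval. The gap concerns named conditions only.
- **A reader might infer that only unprompted Investigator judgement protects the subject.** That is also too strong. Item 2a requires review of adverse events, medications and childbearing status, item 7 makes a risk assessment mandatory for each subject, and the close of item 4 says individual subjects may need assessments where there is clinical concern. Pregnancies are reported and followed (5.6.2, 7.2.7, 9.1.9), so a site would normally know of a delivery. This cover is real but generic: the feasibility decision is tied to safety monitoring and drug supply, the risk assessment concerns participation during the pandemic, and neither names breastfeeding or attaches a consequence to it. For uncontrolled disease the cover is better, which is why that limb is secondary.
- **A reader might want the Part B fracture bar ("Intercurrent known or suspected non-healed fracture at any location") restored too, and might point to item 4, under which "the following assessments can be postponed as determined by the Sponsor and individual site Investigators", including whole-body CT.** Neither holds. The Part B criterion is a known or suspected fracture, which needs no CT, and section 7.3.3 provides only that "WBCT scans will be reviewed for spinal health including fracture assessment". Falls can cause fractures and also trigger trauma dosing (3.1, 3.3), and section 3.3 stresses the risk of under-treatment. Whether to dose with a fracture is therefore a benefit-risk decision, and its absence from Part C is not shown to be an error.

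**Conclusion.** The point holds in a limited form. No explicit Part C or section 7.7 criterion in either protocol defers dosing for breastfeeding, and the item 2b test cannot reveal it. The same omission applies, with less consequence, to uncontrolled significant disease.

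The size is small. Part C takes no new subjects. The only ceilings are planned enrolment of about 60 and about nine, with possible overlap because both studies draw on PVO-1A-201, and subjects restarting at age 14 or over are a subset. The documents do not say how many could be affected; very few is a reasonable expectation. No endpoint, analysis set or estimate changes. This is a minor, low-cost safety correction.

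One assumption is needed. The opening of section 6.4 of PVO-1A-202 is not in the text at hand. The matching part of PVO-1A-204 contains no such bar, and the conclusion assumes that PVO-1A-202 does not add one there.

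**What to change.** In both protocols:

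1. Add breastfeeding and uncontrolled significant disease to 5.4.2 and to the matching synopsis entry, worded as bars to any Part C dosing, daily or flare-up. This also covers restarts after the temporary measures in 7.7 end.
2. Add the same two conditions to 7.7 item 2 as reasons to defer restart, with a direct question on breastfeeding beside the pregnancy test in item 2b.
3. Do not add an automatic fracture deferral. Leave a known or suspected fracture to benefit-risk assessment by the Investigator with the Medical Monitor.

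The cost is a few lines in each protocol and an occasional deferred dose. Recruitment is unaffected because no new subjects are enrolled, and flare-up treatment after a fall with fracture remains possible.

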### **7.3.1 Columbia-Suicide Severity Rating Scale**

In accordance with the Guidance for Industry: Suicidal Ideation and Behavior: Prospective Assessment of Occurrence in Clinical Trials, 2012, all subjects 8 years of age and older who are receiving palovarotene will be assessed for suicidal ideation and behavior every 3 months using the age-appropriate C-SSRS and at all visits during the Flare-up Cycle Safety Assessments (see Appendix 5A). The adult form will be used for subjects 12 years and older and the pediatric form will be used for subjects 8 to 11 years old. Study personnel administering the questionnaire will receive formal training to ensure accuracy and consistency in application of the instrument.

For subjects from Part B continuing non-flare-up-based treatment into Part C, assessment using the C-SSRS will occur every 3 months (Months 3, 6, 9, 12, 15, 18, 21, 24, 27, 30, 33, 36, 39, 42, 45, 48, 51, 54, 57, 60, 63, 66, 69 and 72).

For subjects from Part B starting non-flare-up-based treatment during Part C, assessment using the C-SSRS will occur at Part C Screening and every 3 months (Months 3, 6, 9, 12, 15, 18, 21, 24, 27, 30, 33, 36, 39, 42, 45 and 48). Any subject reporting a type 4 or 5 suicidal ideation or any suicidal behavior within 1 month prior to Part C Screening will not be eligible to receive study drug.

Any subject experiencing a type 4 or 5 suicidal ideation or any suicidal behavior while receiving study drug will have study drug immediately withheld. All such subjects will be referred by the Investigator to a mental health professional for evaluation and counseling as appropriate.

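### Section 7.7 item 2 of both protocols lists no C-SSRS among the minimum checks before palovarotene is restarted at age 14 or older, and nothing applies the past-month suicidality bar to that decision

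*Protocol*

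**What the plan says.** Section 7.7 (Temporary Measures, Study Visits and Assessments) treats subjects aged 14 and older in two stages.

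- **Item 2, not yet restarted.** The list is described as a minimum. In PVO-1A-202 its visit content is "Chronic visits every 3-6 months (per protocol): assess for childbearing status (females only) and pregnancy prevention measures, CAJIS, ConMeds, adverse events, review subject diary", plus PROMIS and FOP-PFQ, which are marked as not required. Timed conditions follow: a pregnancy test within 4 weeks if monthly testing lapsed, laboratory tests within 4 weeks, and radiographs within 12 weeks for subjects who were skeletally immature.
- **Item 3, dosing already resumed.** The remote list in item 3a(i) begins "Chronic visits (per protocol schedule every 3 and/or 6 months): C-SSRS, assess for childbearing status".

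Item 5 (end of treatment or study) also has the scale given remotely: "C-SSRS, assess for childbearing status (females only) and pregnancy prevention measures, CAJIS, Con-Meds, adverse events, PROMIS Global Health Scale, FOP PFQ". PVO-1A-204 has the same structure.

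Elsewhere, both protocols keep certain subjects off drug at first start. Section 5.2.2 no. 13 excludes "Subjects experiencing suicidal ideation (type 4 or 5) or any suicidal behavior within the past month". Section 5.3.2 no. 13 and Section 5.5.2 no. 4 repeat the criterion. Section 7.3.1 of PVO-1A-202 adds that a subject with type 4 or 5 ideation or any "suicidal behavior within 1 month prior to Part C Screening will not be eligible to receive study drug". For subjects already dosed, it says: "Any subject experiencing a type 4 or 5 suicidal ideation or any suicidal behavior while receiving study drug will have study drug immediately withheld".

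**The concern.** Restart after an interruption is a new exposure decision. The protocol requires a structured suicidality check, with a stated consequence, at first start. Item 2 asks for neither at restart, although it sets timed windows for three other safety checks. A subject who developed type 4 or 5 ideation while off drug, or who had recent suicidal behavior, sits between two rules: the entry bar is tied to screening, and the withholding rule applies only to someone taking drug. The stake is that such a subject could be re-dosed without the screen that the sponsor thought necessary the first time.

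**Working it through.** The plan states no figure to reproduce, so the check sets the texts side by side.

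**1. Where the C-SSRS appears in Section 7.7 (same in both protocols).**
- Item 2, before restart: absent.
- Items 3a(i) and 3a(ii), after restart: present at chronic and flare-up visits.
- Item 4, assessments that may be postponed: absent.
- Item 5, end of treatment or study: present.

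**2. Is there a stated reason for the omission?** Remote working does not explain it, because items 3a and 5 give the scale by telephone or video. Deliberate postponement does not explain it, because item 4 does not name it. Low safety priority is also unlikely, because item 2a names two questionnaires that it describes as inessential to safety.

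**3. Does a subject off drug still receive a 3-monthly C-SSRS?** The text points both ways.
- *Yes:* the synopsis of each protocol calls for 3-monthly assessment from age 8 with no on-drug limit. Section 7.2 obliges subjects to follow the schedules, and Tables 1 and 2 list the scale every 3 months.
- *No:* Section 7.3.1 confines it to those "who are receiving palovarotene will be assessed for suicidal ideation and behavior every 3 months", Tables 1 and 2 are titled as schedules during non-flare-up-based treatment, and item 2 leaves it out of its minimum. Section 5.7 asks for continued assessment after discontinuation, but only through reasonable efforts.

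**4. Does either reading close the gap?**
- Under *yes*, a result on schedule can be up to 3 months old at restart, while the bar looks back 1 month. For 3 − 1 = 2 months of each 3-month interval, the last scheduled result is older than the period the bar concerns.
- Under *no*, none is required before restart.
- Under both, no sentence links a result to the decision to restart.

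**5. Which rules keep a subject off drug, and whom do they reach?**
- Sections 5.2.2 and 5.3.2: entry to treatment in Part B (original protocol and Amendment 1 in PVO-1A-204).
- Section 5.5.2 and the eligibility sentence in 7.3.1: subjects starting in Part C (Amendment 3 in PVO-1A-204).
- The withholding sentence in 7.3.1: subjects receiving drug.

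None reaches a subject who is off drug and about to restart.

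**6. Which restarts are already screened?** A restart through flare-up dosing has a C-SSRS at Flare-up Cycle Safety Day 1 (Table 3). For chronic dosing, item 3a(i) lists drug dispensing alongside the C-SSRS, so a site may screen at about the time of restart. The text does not say that the restart supply is dispensed at that contact, or that a negative result must come first.

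**The case against.** The strongest case against is that the protocol follows a consistent design: screen at first start, monitor every 3 months, withhold if positive. No first-start limit is restated in item 2, including those for amylase, lipase, transaminases and triglycerides. Subjects continuing from Part B into Part C meet no suicidality exclusion in Section 5.4.2. Restarts after tetracyclines or CYP3A4 inhibitors carry no C-SSRS condition. Item 2 is only a minimum and refers to the protocol schedule. Before restart there is also adverse event review, a subject-by-subject dosing decision, and ethics committee and competent authority approval.

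Much of this stands. It means that the omission is not a contradiction, and that known suicidality may well be noticed. It does not supply a timed, structured result before the decision. The laboratory comparison is also imperfect: item 2c at least puts the results in the investigator's hands within 4 weeks before restart.

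A reader might infer two stronger claims that the documents do not support. The first is that subjects off drug have no C-SSRS at all, so that the first required one necessarily falls after re-exposure. The synopsis, Section 7.2 and Tables 1 and 2 can be read as requiring one throughout. The second is a measured delay or headcount. The contact that dispenses the restart supply is not stated. Planned enrolment includes children under 14, who are not restarted, and the number of older subjects who stopped is not given.

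**Conclusion.** The point holds as a gap in the restart conditions. Item 2 omits the C-SSRS, and whichever reading of the off-drug schedule is taken, neither a pre-restart window nor the past-month bar is attached to resuming chronic dosing. It rests on the current text of the two protocols. Conditions in the restart approvals or the DMC Charter are not visible and might already cover it.

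Its size cannot be determined from the documents, and no suicidality signal for palovarotene is described in them. It is a minor safety improvement. It does not touch the sample size, the type I error rate or the primary analysis.

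**What to change.** Add to Section 7.7 item 2 of both protocols: *C-SSRS (adult Since Last Visit form, given remotely) no more than 4 weeks before palovarotene is restarted, recording the date of any positive item; do not restart if type 4 or 5 ideation or suicidal behavior of any kind occurred in the past month, and refer as in Section 7.3.1.*

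The 4-week window matches items 2b and 2c. Appendix 5A assigns the Since Last Visit form to visits after Screening from age 12, so it suits every restarting subject. Dates are needed because neither adult form asks about behavior over exactly one month: the Screening form looks back 1 year, and the other looks back to the last visit.

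The cost is one line per protocol, one remote questionnaire per restarting subject, and possibly a few delayed restarts. Staff already give the scale remotely under items 3a and 5.
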